# - Safety Endpoints:

- Adverse events
- Serious adverse events

**Procedures and Assessments:** Efficacy and Safety procedures and assessments for this study will include all the listed enpoints as well as the recording of concomitant medications' use.

**Overall Study Design:** this clinical trial is designed as an adaptive, randomized, controlled, multicentre study to evaluate efficacy and safety of Reparixin in hospitalized adult patients with severe COVID-19 pneumonia. In the phase 2 segment of this study, patients will be randomized 2:1 to Reparixin oral tablets 1200 mg (Group 1, active treatment) or standard of care (Group 2, control arm). In case of worsening (e.g. need of ICU and/or mechanical ventilation) after the first 24hrs, patients will be offered a rescue medication based on their physicians' judgement, without any constrain from the sponsor. The administration of rescue medications is allowed, without constituting a protocol deviation. In the phase 3 segment of this study, it is planned that patients will be randomized 2:1 to Reparixin or standard of care. In case of worsening after the first 24hrs, patients under the control arm will be offered a rescue medication with the active treatment (Reparixin 1200 mg oral tablets TID) or Reparixin 2.772 mg/kg body weight/hour IV infusion, if the oral route is unfeasible for the clinical condition. The Phase 3 design will be reassessed and decided based on the results of the Phase 2.

**Population:** Hospitalized adult ( $\geq$ 18 <90 years old) patients with severe COVID-19 pneumonia. No gender and/or ethnicity restrictions will apply.

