# 9 STATISTICAL CONSIDERATIONS

#### 9.1 Sample size

The sample size for this trial will be adaptively determined through a phase 2/3 design. Enrollment is planned to last approximately 2 months. Each patient will be randomly allocated to Reparixin or Control according to a randomization ratio of 2:1 and he/she will be followed for the entire treatment and follow-up duration for collecting the efficacy endpoints of each study phase.

For the Phase 2 portion of the study, the primary analysis will compare Reparixin versus Control in terms of time to a composite endpoint (primary endpoint of phase 2) including the following events: requirement of supplemental oxygen treatment, mechanical ventilation use, admission to ICU, and any requirement of rescue medication. Based on clinical experience, an improvement of the median time freedom from composite event of 1.5 times is expected. Assuming an exponential distribution, a total sample size of 48 patients will allow to provide 80% power to show superiority of Reparixin compared to control using a log-rank test at a one-sided significance level of 0.025.

The sample size for the phase 3 is based on assessment of superiority of Reparixin compared to control arm in terms of freedom from a composite endpoint (primary endpoint of phase 3) of severe events including death, admission to the ICU, requirement of mechanical ventilation.

Based on same assumptions of phase 2 regarding randomization (2:1) and expecting to double the median time freedom from severe composite event using Reparixin compared to control (from 2-4 to 4-8 days), a total sample size of 111 patients will allow to achieve a power of 90% to show superiority of Reparixin over control using a log-rank test at a one-sided significance level of 0.025. No drop-out are expected to happen. The number of patients to be included may be revised based on considerations from Phase 2 data analysis.

Primary endpoint of phase 3 will be tested only if superiority of Reparixin is shown in phase 2. Thus, the overall type I error of the study will be controlled at 0.025 via the hierarchical testing procedure.

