### 9.4.2 Analysis of efficacy variables

#### 9.4.2.1 Primary analysis of phase II

In phase II, the primary endpoint to assess the efficacy of Reparixin versus the Control is the time freedom from a composite endpoint of events including supplemental oxygen treatment, mechanical ventilation use, admission to ICU, and any use of rescue medication. The time to the first event (any one of the components defined in the phase II composite endpoint) will be used for analysis. In case of no events, the rules for censoring defined in section 9.4.1 will be used.

The primary endpoint will be evaluated by means of Kaplan-Meier estimates and log-rank test. The null hypothesis H0phaseII is that the freedom form events in Reparixin (TREPARIXIN) is lower or equal than control (TCONTROL):

H0phaseII: TREPARIXIN ≤ TCONTROL H1phaseII: TREPARIXIN > TCONTROL

where TREPARIXIN and TCONTROL are the freedoms from event for Reparixin and Control, respectively. The null hypothesis H0phaseII will be rejected, and superiority of Reparixin concluded (alternative hypothesis H1phaseII) if log-rank p-value will be lower than pre-specified threshold, depending at which analysis (interim or final) the test is performed. Thresholds are calculated according to O'Brien-Fleming spending function boundaries and tare reported in Table 1.

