3.5 Efficacy endpoints

3.5.1 Primary endpoints

- Primary Endpoint for phase 2: Composite endpoint of clinical events (the subject requires at least one of the following: supplemental oxygen requirement, invasive mechanical ventilation use, admission to ICU, and use of a rescue medication for any reason);
- Primary Endpoint for phase 3: Composite endpoint of death and clinical severe events (the subject dies or requires invasive mechanical ventilation use and/or admission to ICU).

3.5.2 Secondary Endpoints:

- Clinical severity score (a seven-category ordinal scale) at any available time point
- Dyspnea severity (Liker categorical scale and VAS continuous scale) at any available time point;
- Changes in body temperature at any available time point;
- Duration and quantity of supplemental oxygen treatment at any available time point;
- Incidence and duration of mechanical ventilation use at any available time point;
- Incidence of ICU admission need at any available time point;
- Lung damage extension changes from baseline (assessed by Chest CT or Rx) at any available time point;
- Change from baseline in lung exudation degree (assessed by Chest CT or Rx) at any available time point;
- PaO₂ at any available time point;
- SpO₂ at any available time point;
- Partial arteriolar oxygen pressure (PaO₂) to fraction of inspiration O₂ (FiO₂) ratio at any available time point;
- CRP at any available time point;
- Hs-CRP at any available time point;

3.5.3 Exploratory Endpoints (not mandatory):

- Cytokine profile at any available time point;

- Concentration of reparixin in serum over time;
- SARS-CoV-2 virologic counts at any available time point.

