Composite endpoint of phase 2 and Time to event (days)	
From ADDITIONAL INFORMATION form:
 
 • if “Has the patient been admitted to the ICU?” = “Yes”, then component1 = “Yes” and date of event1 = Date of Visit • if “Has the patient been admitted to the ICU?” = “No”, then component1 = “No” 
From PATIENT STATUS form:
 
 • if “Is the subject eligible to switch to rescue medication?” = “Yes”, then component2 = “Yes” and date of event2 = Rescue treatment start date 
 ○ If Rescue treatment start date is missing, then Date of Visit will be used • if “Is the subject eligible to switch to rescue medication?” = “No”, then component2 = “No” 
From ADDITIONAL INFORMATION and MECHANICAL VENTILATION forms:
 
 • If “Has the patient been mechanically ventilated?” = “Yes” and type = “Invasive mechanical ventilation”, then component3 = “Yes” and date of event3 = mechanical ventilation start date 
 ○ If mechanical ventilation start date is missing, then Date of Visit will be used • If “Has the patient been mechanically ventilated?” is not empty and type ≠ “Invasive mechanical ventilation”, then component3 = “No” 
From “Worsening based on PaO₂/FiO₂” (see above):
 
 • if a patient is classified as “Worsened”, then component4 = “Yes” and date of event4 = Date of Visit • if a patient is classified as not “Worsened” (excluding missing classification), then component4 = “No” 
The composite endpoint is equal to “Yes” if at least one post-baseline component (1-4) is equal to “Yes” and the date of event is the corresponding date of event. In case of more component equal to “Yes”, the first date will be used.
 
Otherwise, if all component (1-4) are equal to “No” the composite endpoint will set as “No”. The date of event will be last date where is known that all components are equal to “No”.
 
Time to composite endpoint (days) = Date of event - Date of randomization

Parameter	Derivation

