Time to supplemental oxygen requirement (days)	Time to supplemental oxygen requirement (days) = First Administration start date - Date of randomization
Time to mechanical invasive ventilation use (days)	Time to (invasive) mechanical ventilation use (days) = First (invasive) Mechanical Ventilation start date - Date of randomization
Time to admission to ICU (days)	Time to admission to ICU (days) = Admission date - Date of randomization
Time to rescue medication (days)	Time to rescue medication (days) = First rescue treatment start date - Date of randomization
Overall survival (days)	Overall survival (days) = Date of death - Date of randomization
Subject with improvement based on Likert scale	Improvement = any of these answers: 
 • 1 = minimally better, • 2 = moderately better, and • 3 = markedly better
Cumulative quantity (L) of oxygen treatment	Cumulative quantity of oxygen treatment (L) = Sum of all Quantity (L) in CONCOMITANT OXYGEN TREATMENT form, from randomization to time point of interest. It is defined as supplemental oxygen requirement any increased used of oxygen compared to baseline.
Cumulative duration (hours) of oxygen treatment	Cumulative duration of oxygen treatment (hours) = Sum of duration of oxygen administration (hours) in CONCOMITANT OXYGEN TREATMENT form, from randomization to time point of interest. Duration of oxygen administration (hours) = Administration end date/time - Administration start date/time / 60
Cumulative duration (hours) of mechanical ventilation	Cumulative duration of mechanical ventilation (hours) = Sum of duration of mechanical ventilation (hours) in MECHANICAL VENTILATION form, from randomization to time point of interest. Duration of mechanical ventilation (hours) = End date/time - Start date/time / 60
Duration (days) of ICU stay	Duration of ICU stay (days) = Discharge date - Admission date
Change from baseline	For changes from baseline the baseline value will constitute the minuend and the later value the subtrahend.
Conversion of Time Intervals	If a time interval was calculated in minutes, hours or days and needs to be converted into months or years the following conversion factors will be used: 
 • 1 hour = 60 minutes • 1 day = 24 hours • 1 week = 7 days • 1 month = 30.4375 days • 1 year = 365.25 days

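### SAP Table 7 scores the phase 2 rescue component from an eligibility question and does not require that rescue was given

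*SAP*

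**What the plan says.** **The endpoint.** SAP 3.5.1 defines the rescue component of the phase 2 composite as "use of a rescue medication for any reason". Protocol 9.4.2.1 agrees, listing "admission to ICU, and any use of rescue medication". Protocol 9.1 is looser: "any requirement of rescue medication".

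**The derivation.** In SAP 9.1, Table 7, component 2 takes its value from one question on the PATIENT STATUS form: "Is the subject eligible to switch to rescue medication". Yes gives Yes and No gives No. The event date is the rescue start date, with this fallback: "If Rescue treatment start date is missing, then Date of Visit will be used". One post-baseline Yes among the four components makes the composite an event. The same rule is repeated for the modified composite (with death added) and for the composite that uses the oxygen delivery system classification.

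**The separate rescue variable.** Later in Table 7: "Time to rescue medication (days) = First rescue treatment start date - Date of randomization". SAP 7.1.3.1 analyses this component as first use of rescue.

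**The setting.** SAP 3.3 and protocol 9.4.5 call the trial open-label. In phase 2, on worsening, "patients will be offered a rescue medication based on their physicians' judgement, without any constrain from the sponsor" (protocol 1, Overall Study Design). SAP 7.1.3.1 bases the decision on phase 3 on the primary analysis alone, whatever the sensitivity analyses show. SAP 4.9 reports no change to the planned analysis and clarifies only the oxygen component.

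**The concern.** Being eligible for a drug and receiving it are different data. The endpoint is the second; the derivation records the first. The other components taken from form questions ask about facts: whether the patient was admitted to the ICU, and whether the patient was ventilated. The visit-date fallback for ventilation applies only after ventilation has been confirmed. For rescue, the fallback applies after eligibility alone.

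Phase 2 rescue is left to physicians who know the arm, no criteria are set, and no blinded adjudication of the component is described. If eligibility were judged more readily in one arm, the phase 2 test would absorb that difference. The two other phase 2 composites copy the rule, so neither tests it. The analysis of the single component could expose the discrepancy but cannot change the go/no-go decision.

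**Working it through.** **1. The rule applied to the four possible patients.**

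| Eligibility answer | Rescue given? | Table 7 component 2 | Endpoint as defined (use) |
|---|---|---|---|
| Yes | Yes, date recorded | Event at start date | Same |
| Yes | Yes, date missing | Event at visit date | Event; visit date is a reasonable imputation |
| Yes | No | Event at visit date | No rescue event |
| No | Yes | No event | Event at start date |

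Rows 1 and 2 are sound. Rows 3 and 4 are wrong in opposite directions. A row 3 patient also has no value for the separate time-to-rescue variable, because there is no start date.

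**2. The plan's own figure.** Inputs from SAP 3.2 and Table 4: 46 events, 48 subjects, 2:1 allocation, 21 days of follow-up, 2 versus 5 days to the phase 2 endpoint, one-sided 0.025, one interim at 23 events. I read 2 and 5 days as exponential medians, so the hazard ratio (HR) is 2/5 = 0.40.

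- Drift = sqrt(46 × 2/3 × 1/3) × |ln 0.40| = 3.197 × 0.916 = 2.93. Fixed-design power = Φ(2.93 − 1.96) = 83.4%.
- Through the two looks of Table 4 with futility obeyed, power is 80.1%. This reproduces the stated figure of about 80%.
- The protocol's 1.5-fold improvement gives only about 23% in the same calculation, so I use the SAP's assumption. That conflict is a separate matter.

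**3. Room for added events.** Expected events = 16 × (1 − 2^(−21/2)) + 32 × (1 − 2^(−21/5)) = 15.99 + 30.26 = 46.2. Only 48 − 46.2 = 1.8 patients are expected to stay event-free. Under the planning assumptions, row 3 can therefore add about 2 events at most. For everyone else it can only move the first event earlier. If the true event rate is lower than planned, there is more room to add events.

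**4. Direction, by illustration.** The documents give no rate of eligible-but-untreated answers. As an assumption, let such answers arrive at an extra hazard f equal to 10%, 25% or 50% of the control hazard, independently of the other components.

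- *Equal in both arms.* HR = (0.40 + f)/(1 + f) = 0.455, 0.52, 0.60. Two-look power at 46 events falls from 80.1% to 67.5%, 51.6%, 34.3%.
- *Control arm only, no true effect.* I used 20,000 simulated single-look log-rank tests with 16 + 32 patients and a 2-day median. One-sided rejection rises from a simulated baseline of 3.5% (nominal 2.5%) to 6.1%, 12.1%, 27.7%.

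These runs show only that the rule can push either way. They do not estimate its effect in this trial. If eligibility tends to coincide with ICU admission or ventilation, the effect is smaller.

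**The case against.** - **The field may mean the switch itself.** SAP 5.4, Patient status, tabulates subjects switching to rescue and lists no separate eligibility item. The form is not available, so this cannot be settled. A reader might infer that a physician's opinion with no drug given is certain to be counted; the documents do not establish that, nor do they say who answers the question. The objection stands as a reason to clarify. It does not remove the problem, because Table 7 does not limit the rule to drug given.
- **The fallback looks like ordinary missing-date imputation.** That is a fair reading, and the same fallback appears for ventilation. There, however, the event has first been confirmed.
- **The wording is mixed.** The endpoint definitions open with what the patient requires, and protocol 9.1 speaks of requirement. The analysis definitions in protocol 9.4.2.1 and SAP 3.5.1 nevertheless name use.
- **Date mismatch is not special to rescue.** The composite dates ICU admission at the visit, while the separate ICU variable uses the admission date. This is correct, so the case rests mainly on what counts as an event.
- **Actual rescue is also open to physician judgement.** This stands. Scoring administration does not remove open-label bias; it removes only the part that the derivation adds.
- **Other safeguards exist.** SAP 7.1.2 has the phase 3 composite, which contains no rescue, analysed in phase 2 as secondary. A superiority claim needs both phases to succeed, and the phase 3 primary has no rescue component. These points limit the damage but do not alter the go/no-go rule.

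**Conclusion.** The derivation does not implement the endpoint as defined and should be corrected before the phase 2 primary analysis. Followed literally, it counts eligibility without use, dates it at the visit, and misses use without eligibility.

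Its size cannot be stated, because the documents give no rate for either error. A reader might take some number of eligible-but-untreated patients, divide by 46 and call the result the share of false events. That is not supported: any such number is an assumption, and in a first-event composite with about 46 events planned in 48 patients the usual consequence is an earlier date, not an extra event. A reader might also infer that the rule favours reparixin. It does so only if eligibility is called more readily in the control arm, which nothing in the documents shows. Non-differential miscoding lowers power and works against reparixin.

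The conclusion rests on the Table 7 text as written. If the form's question in fact records an actual switch, the fault reduces to unclear wording, to be put right by stating that.

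**What to change.** In Table 7, for the phase 2 composite, the modified composite and the oxygen-delivery composite:

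1. Set component 2 to Yes only when administration of rescue is documented, by a rescue treatment start date or by a medication record classified as rescue. Date the event at that start.
2. Use the visit date only when administration is confirmed but undated.
3. Make the classification of medication records at the data review meeting (SAP 4.10), without knowledge of outcome by arm. This step is needed because standard of care is not prespecified and the choice of rescue is unrestricted (protocol 6.2), so a drug name alone may not identify rescue. That meeting is planned before the final lock; apply the same classification to the interim data if the interim is still to come.
4. Keep the eligibility-based scoring as a prespecified sensitivity analysis, and report how many patients fall in rows 3 and 4 of the table above, by arm.

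The data are already collected: rescue start date in Table 7, concomitant medication with start and end dates in protocol 6.4. The cost is a small amount of extra programming and one classification step. The downside is possibly slightly fewer or later events. No clinical rule on rescue changes.

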#### 5.2 Inclusion/exclusion criteria

#### Phase 2 Inclusion Criteria:

- 1. Age 18 to 90.
- 2. Confirmed COVID-19 diagnosis
- At least one of the following: ① Respiratory distress, RR ≥ 30 breaths/min without oxygen; ② Partial arterial oxygen pressure (PaO2) / Fraction of inspiration O2 (FiO2) >100 <300mmHg (1mmHg = 0.133kPa).

- 4. Chest imaging confirms lung involvement and inflammation.
- Inflammatory status as documented by at least one of the following: Lactate dehydrogenase (LDH) > normal range, C-reactive protein (CRP) ≥ 100mg/L or IL-6 ≥ 40pg/mL, serum ferritin ≥ 900ng/mL, XDP >20mcg/mL.

Phase 3 Inclusion Criteria: same as above; other criteria TBD based on Phase 2 outcomes.

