## Phase 2/3 Exclusion Criteria:

- 1. Cannot obtain informed consent.
- Severe hepatic dysfunction (Child Pugh score ≥ C, or AST> 5 times the upper limit); Severe renal dysfunction (estimated glomerular filtration rate ≤ 30mL / min / 1.73 m2) or receive continuous renal replacement therapy, hemodialysis, or peritoneal dialysis. Serum albumin <2.5 g/dL.

- 3. Patients with hypersensitivity to ibuprofen or to more than one non steroidal anti-inflammatory drug or to more than one medication belonging to the class of sulfonamides (e.g. sulfamethazine, sulfamethoxazole, sulfasalazine, nimesulide or celecoxib; hypersensitivity to sulphanilamide antibiotics alone, e.g. sulfamethoxazole, does not qualify for exclusion)
- 4. Severe, active bleeding such as hemoptysis, gastrointestinal bleeding, central nervous system bleeding, and nosebleeds within 1 month before enrollment.
- 5. Pregnant and lactating women and those planning to get pregnant.
- 6. Participated in other interventional clinical trials with investigational medicinal products, not considered suitable for this study by the researchers.
- 7. At the time of enrollment, patients not in a clinical condition compatible with the oral administration of the study drug.

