#### 6.2 Control treatment

#### Phase 2/3 Control treatment

Control group in both the phase 2 and 3 segments will be standard of care, which due to the nature of the COVID-19 pandemic is expected to evolve over time and, thus, cannot be prespecified. This group will be populated in a prospective manner and offered a rescue medication in case of worsening (e.g. need of ICU and/or mechanical ventilation). Due to the evolving understanding of novel treatments being currently tested during the COVID-19 pandemic, the Sponsor will not put any restriction on the selection of the rescue medication during phase 2. In the phase 3, Reparixin will be offered as rescue medication, as oral tablets or as IV infusion in case of unfeasibility of the oral administration due to the clinical conditions (e.g. intubated patients in the ICU).

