#### **Dose and Route of Administration**

Oral tablets: For patients able to comply with the oral treatment, it is recommended to take for each administration two Reparixin 600 mg tablets, for the total of three daily administrations. It is advisable to take the tablets with a glass of water to facilitate swallowing. For patients who are unwilling or unable, in the opinion of the investigator, to comply with the oral tablets treatment, is possible to administration, disperse two Reparixin 600 mg tablets in 25 mL of drinking water in a suitable container (e.g. conical tubes for 50 mL Falcon centrifuge). Disgregate the tablets (shaking manually or with the aid of a planetary shaker or a rocker) until obtaining a homogeneous milky suspension (time required 7 - 10 minutes). Keep the prepared suspension at room temperature and protected from light for up to 24 hours. Immediately before administration, manually shake the suspension again until complete and homogeneous resuspension, withdraw using a 50 mL needle-free syringe and administer to the patient using a naso-gastric tube.

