5.8 Other baseline characteristics

The following information at baseline will be descriptively reported by means summary statistics:

- Clinical severity score (categorical)
- Dyspnea VAS scale (continuous)
- Respiratory parameters (continuous)
 - FiO₂ (%)
 - Respiration rate (Breath/min)
 - PaO₂ (mmHg)
 - SpO₂ (%)
 - PaO₂/FiO₂ (Ratio)
 - Acute Respiratory Distress Syndrome (ARDS) severity and their categorical evaluation, if applicable.
- Additional information
 - Did the subject experience any Adverse Events? (yes, no);
 - Has the subject been admitted to the ICU? (yes, no);
 - Was oxygen administered to the subject? (yes, no);
 - Has the subject been mechanically ventilated? (yes, no).

6. Evaluation of Treatment Compliance and Exposure

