
Composite endpoint of phase 3 and time to event (days)
	
From ADDITIONAL INFORMATION form:
 
 • if “Has the patient been admitted to the ICU?” = “Yes”, then component1 = “Yes” and date of event1 = Date of Visit • if “Has the patient been admitted to the ICU?” = “No”, then component1 = “No” 
From ADDITIONAL INFORMATION and MECHANICAL VENTILATION forms:
 
 • If “Has the patient been mechanically ventilated?” = “Yes” and type = “Invasive mechanical ventilation”, then component3 = “Yes” and date of event3 = mechanical ventilation start date 
 ○ If mechanical ventilation start date is missing, then Date of Visit will be used • If “Has the patient been mechanically ventilated?” is not empty and type ≠ “Invasive mechanical ventilation”, then component3 = “No” 
From DEATH REPORT form:
 
 • If “Date of death” is not missing, then component5 = “Yes” and date of event5 = date of death • Otherwise component5 = “No” 
The composite endpoint is equal to “Yes” if at least one post-baseline component (1, 3 and 5) is equal to “Yes” and the date of event is the corresponding date of event. In case of more component equal to “Yes”, the first date will be used.
 
Otherwise, if all component (1, 3) are equal to “No” the composite endpoint will set as “No”. The date of event will be last date where is known that all components are equal to “No”.
 
Time to composite endpoint (days) = Date of event - Date of randomization

Parameter	Derivation

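### SAP Table 7 has no new-onset condition for ICU admission, so a patient already in ICU at randomization becomes an event at the first post-baseline visit in both primary composites

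*SAP*

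**What the plan says.** **Eligibility.** Protocol 5.2 defines severity at entry by respiratory rate or by "Partial arterial oxygen pressure (PaO2) / Fraction of inspiration O2 (FiO2) >100 <300mmHg". No inclusion or exclusion criterion names ICU stay or ventilation. The nearest exclusion is "At the time of enrollment, patients not in a clinical condition compatible with the oral administration of the study drug". The phase 3 criteria are given as "same as above; other criteria TBD based on Phase 2 outcomes".

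**Dosing text that bears on eligibility.** Protocol 6.2 foresees IV rescue in phase 3 "in case of unfeasibility of the oral administration due to the clinical conditions (e.g. intubated patients in the ICU". Protocol 6.3, for patients who cannot manage tablets, describes dispersing them in water and says to "administer to the patient using a naso-gastric tube".

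**Endpoint derivation (SAP 9.1, Table 7).** If the visit form says the patient has been admitted to ICU, the ICU component is positive and takes the visit date. Only invasive ventilation counts. It takes its own start date, and the visit date only if the start date is missing. For phase 2, "The composite endpoint is equal to “Yes” if at least one post-baseline component (1-4) is equal to “Yes", and then "Time to composite endpoint (days) = Date of event - Date of randomization". The phase 3 row, the modified phase 2 row and the oxygen-delivery row repeat the ICU and ventilation rules.

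**Baseline information.** SAP 5.8 tabulates "Has the subject been admitted to the ICU? (yes, no" at baseline, along with mechanical ventilation. SAP 4.9 defines supplemental oxygen relative to baseline because patients were expected to enter on oxygen. It says nothing similar for ICU or ventilation. Table 7 derives time to ICU admission from the admission date, but the composites do not use that date.

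**The concern.** The word post-baseline in Table 7 selects which record is read. It does not require a change since baseline. A patient in ICU on high-flow oxygen with a PaO2/FiO2 ratio of 200 meets the severity criterion and, if still in ICU at Day 1, is an event that neither arm could have prevented.

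Such events arise at the same rate in both arms and pull the curves together. SAP 3.2 expects 46 events in about 48 patients, and phase 3 is tested only if phase 2 succeeds. These events also come early. If 20% of the roughly 27 patients at the phase 2 interim entered in ICU, 0.20 × 27 = 5.4 of the 23 trigger events would reflect entry status.

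The planned supporting analyses do not correct this. The modified composite and the oxygen-delivery composite reuse the ICU rule. The Cox model in SAP 7.1.3.1 adjusts for the clinical severity score, whose seven categories do not include ICU stay, and the same section bases the decision to proceed on the primary analysis alone.

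**Working it through.** **1. The plan's own figures.** Inputs: 2:1 allocation, one-sided 0.025, medians of 2 and 5 days in phase 2 and a doubled median in phase 3 (SAP 3.2, Table 2; Protocol 9.1), 21 days of follow-up, no drop-out.

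Events for a fixed design: d = (z_α + z_β)² / [(1/3)(2/3)(ln HR)²].

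- Phase 2, HR = 2/5 = 0.40, 80% power: (1.960 + 0.842)² / (0.2222 × 0.8396) = 42.1, so 43 events.
- Phase 3, HR = 0.50, 90% power: (1.960 + 1.282)² / (0.2222 × 0.4805) = 98.4, so 99 events.
- With the boundaries of SAP Tables 4 and 5, 46 events give 80.2% power and 109 events give 90.3%.
- Expected events: N[(1/3)(1 − 2^(−21/m_c)) + (2/3)(1 − 2^(−21/m_t))]. This gives 46.2 for N = 48 at 2 and 5 days, and 109.0 for N = 111 at 2 and 4 days.

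The plan's event counts therefore reproduce. The protocol's 1.5-fold phase 2 effect does not (it would need 215 events). That is a separate matter, and the SAP effect is used below.

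**2. The rule as written.** Log-rank trials were simulated with exponential event times and a single look at the final threshold (0.024 in phase 2, 0.02151 in phase 3). A share f of each arm is in ICU at entry and is scored as an event at day 1. The documents give no value for f, so 0 to 30% is an assumption. The 3 vs 6 day scenario is the middle of the SAP range.

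| Power, % | f = 0 | 10% | 20% | 30% |
|---|---|---|---|---|
| Phase 2, 2 vs 5 days, whole days | 83 | 74 | 62 | 51 |
| Phase 2, continuous time | 84 | 75 | 68 | 59 |
| Phase 3, 3 vs 6 days | 90 | 85 | 76 | 66 |
| Phase 3, 2 vs 4 days, continuous time | 92 | 86 | 79 | 73 |
| Phase 3, 4 vs 8 days, continuous time | 90 | 83 | 75 | 67 |

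Whole days means times rounded up to the day, which is closer to Table 7, where time is a difference of dates.

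**3. Under the null.** The rejection rate was 0.034 to 0.038 in phase 2 (0.034 at f = 0) and 0.027 to 0.030 in phase 3, with no trend in f.

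**4. After requiring new onset.** Phase 2 power depends on how patients in ICU at entry are then handled.

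| Handling | f = 10% | 20% | 30% |
|---|---|---|---|
| Left out of the analysis | 77 | 73 | 67 |
| Kept, failing on other components at half the hazard | 80 | 77 | 75 |
| Kept, never failing otherwise | 42 | 27 | 18 |

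The last row falls below the rule as written because patients who cannot fail stay in both risk sets to day 21 and flatten the contrast between arms.

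**5. Ventilation.** For a patient on invasive ventilation at entry, the event date is a start date before randomization. Date of event minus date of randomization is then negative, and the SAP has no rule for that.

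**The case against.** The strongest reply is that ICU need is the protocol's example of worsening after entry, and the endpoint is worded as an admission, which is an event rather than a state. On that view the form's question may mean since the last visit. The case report form is not available, so this cannot be excluded, and it limits confidence. But the SAP does not say so, and it tabulates the same question at baseline.

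A reader might infer that the documents expect ICU patients at entry because ICU and ventilation are recorded at screening and baseline. They do not show this. The schedule marks almost every clinical item at every visit, including a dyspnea scale that compares breathing with the start of the drug. What stands is that such patients are not barred.

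A reader might also infer that patients ventilated at entry become events at the first visit. Table 7 does not do that unless the start date is missing. It is also doubtful that they can be enrolled: Protocol 6.2 names intubated patients as an example of unfeasible oral dosing, which points to the oral-dosing exclusion, while the naso-gastric instruction in 6.3 points the other way.

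Finally, phase 3 entry criteria are still open, and SAP 4.7 foresees an amendment and an updated SAP. That leaves time to act on phase 3 but does not help phase 2.

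**Conclusion.** The point holds for the ICU component of both primary composites. Following Table 7 as written, a patient in ICU at entry and still there at the first post-baseline visit is an event by reason of entry status.

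The consequence is dilution. At an assumed 10 to 30% in ICU at entry, phase 2 power falls from about 83% to between 74% and 51%, and phase 3 power from about 90% to between 85% and 66%. If nobody enters in ICU, nothing is lost. These figures rest on the SAP's effect sizes, an equal expected share in both arms, and events scored at day 1.

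Two stronger readings are not supported. Entry-status events do not raise the false-positive rate, since rejection under the null shows no trend with their share. Nor is the loss at least as large in phase 3, although ICU and ventilation are two of its three components: at 10/20/30% it is about 5/14/24 points, against 9/21/32 in phase 2.

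Invasive ventilation at entry is a lesser gap, namely a possible negative time without a rule. Overall this should be fixed. Confidence is medium, because neither the form's wording nor the ICU share is in the documents.

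**What to change.** In every composite row of Table 7, count ICU admission and invasive ventilation only when absent at baseline and starting after randomization. Date the ICU component by the admission date that Table 7 already uses for the single-component time. Before database lock, state how patients with either status at baseline are analysed, and add a sensitivity analysis of the primary endpoint in patients not in ICU at baseline.

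The eligibility text and the endpoint definition should be reconciled in the phase 3 amendment already foreseen in SAP 4.7, including whether the oral-dosing exclusion covers intubated patients.

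The programming cost is one condition on baseline data already collected. The statistical cost is fewer counted events, and it may not be small. As the second table in the working shows, power after the change can be better or much worse than under the present rule, depending on how often patients in ICU at entry fail on other components. The handling should therefore be chosen and justified in advance.
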